The QLQ-BR23 is a broadly used questionnaire that has been validated in Danish [34, 35]. The questionnaire includes several items of interest, but specifically for the present study, we focus on breast symptoms as a primary outcome. The remaining items from the questionnaire will be considered secondary outcomes, as described below. The QLQ-BR23 questionnaire will be filled out by the patients once weekly for the duration of the radiation therapy, and once weekly for three weeks after the last radiation fraction.

Secondary outcomes

The QLQ-C30 is a questionnaire concerning the quality of life in cancer patients in general, which is widely used and has been validated in Danish [36]. All items in the QLQ-C30 as well as the items from QLQ-BR23 (above) that are not mentioned under primary outcomes will be considered secondary outcomes. Patients will be asked to answer both questionnaires at baseline, once weekly during radiation therapy, and once weekly for three weeks after the last radiation fraction.

Patients will be asked about steroid cream usage for radiation dermatitis at baseline, once weekly during radiation therapy, and once weekly for three weeks after the last radiation fraction.

Demographic and background variables will be collected at baseline (see table 2 for a full list of demographic and background variables).

Participant timeline

The participant timeline is outlined in table 3. At the pre-screen consent, the patients will be informed that they have a right to 24 hours of consideration prior to deciding to participate in the trial or not. Oral and written consent will be obtained by the primary investigator at the time noted

in table 3, or at a maximum 24 hours hereafter. There will be no study-specific post-trial care for the participants, other than following the standard treatment regimens offered at Rigshospitalet.

Randomization and blinding

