Prior to the first radiation treatment patients will receive a tube of cream with a number corresponding to their randomization number. They will be instructed in storage of the tube as described above. Patients will be seen once weekly throughout their radiation therapy. At this meeting, the patients will be asked how much cream they have left, and another tube of cream will be handed out when the patients are expected to run out of cream before the next meeting. Patients will receive a total of two to three tubes, depending on the number of radiation fractions they receive, each containing 30 g of cream.

Patients will be instructed to apply the cream twice daily, once in the morning and once in the evening. The patients will be instructed to apply approximately 1 g of cream in the treatment area twice daily. On days where the patients receive radiation fractions, the patients will be instructed to apply the morning dose no less than 2 hours prior to radiation. As part of the instruction, the investigator will weigh out 1 g of cream, so that the patient can see what amount of

cream they should apply each time. During the weekly visits, the patients will be asked if they are experiencing trouble applying the cream, and the investigator will help guide them. At every visit the patients will be asked to bring with them the tube of cream they are currently using. When first handed out, and during each visit, the tube will be weighed on a high-precision scale (range 0.01 mg to 200 g). Usage of cream will be calculated, usage will be evaluated. Furthermore, along with the first tube of cream, the patients will receive a schedule with the relevant dates for the patient; the patient will have to fill in every time they have applied the cream. When a patient is expected to run out of cream before the next visit, another tube will be handed to them. One tube of cream contains 30 g of cream, and the patients will apply 2 g each day they receive radiation. One tube should last for 15 days, assuming they administer the correct dose daily, and assuming they are able to completely empty the tube. Ideally patients will receive new tubs on Study visit week 2 and 4, if they have managed to use the instructed dose.

Statistics

Sample size calculations

In order to establish the needed number of patients for the study, we have performed 3 separate sample size calculations.

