The sample size calculation for the RTOG acute radiation morbidity scoring criteria is based on the findings in a previous study examining melatonin as a radiation protector of the skin in patients receiving radiation therapy for breast cancer [11]. In this study, at two weeks follow-up, 41% of the patients receiving melatonin had toxicity grade 1-2 vs 90% of the patients receiving placebo.

Incidence in placebo group: 90%

Incidence in melatonin group: 41%

Alpha: 5%

Beta: 20%

Sample size needed: Two groups of 14 patients, totaling 28 patients.

The sample size calculation for the image analysis is based on the study evaluating erythema after exposure to ultraviolet radiation [33]. Data for the sample size calculation were obtained directly from the authors. We make the assumption that the erythema based on ultraviolet radiation can be a reasonable substitute for acute radiation dermatitis based on erythema being a part of the RTOG acute radiation morbidity scoring criteria grade 1 and 2 [30]. Based on the study used for the RTOG sample size calculation, we assume that the erythema will be most pronounced 2 weeks after conclusion of radiation therapy. We also make the assumption that melatonin applied twice daily in a 2.5% cream in which it is completely dissolved, will provide an effective dose comparable to the 12.5% used in the study evaluating ultraviolet radiation [17], due to a deposition or depot-effect in the skin [37]. Furthermore, we have been informed by the authors of the previous study utilizing the 12.5% cream that the cream was not homogenous, and contained small granules of undissolved melatonin in both the 2.5%, 5% and 12.5% creams. This suggests that the required dose, to obtain an effect, is in fact smaller than 12.5%. The sample size is calculated based on the a^* -values, where a high a^* -value corresponds to a higher degree of erythema.

Mean (SD) a^* -value for placebo at all time points: 18.4 (3.47)

Mean (SD) a^* -value for 12.5% melatonin cream at all time points: 13.44 (2.36)

Alpha: 5%

Beta: 20%

Sample size needed: Two groups of 8 patients, totaling 16 patients.

The sample size calculation for the QLQ-BR23 breast symptom score is based on a study investigating quality of life following radiation therapy, comparing mastectomy to breast conservation therapy in patients with breast cancer [38]. The data used for the sample size-

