calculation are based on the patients receiving breast-conserving therapy, on their last day of radiation. The 142 patients scored a breast symptom score mean (SD) of 82.2 (15.1).

Mean (SD) a*-value for breast symptoms: 82.2 (15.1)

We aim to reduce the breast symptom score to 70.

Alpha: 5%

Beta: 20%

Sample size needed: Two groups of 24, totaling 48 patients.

Because we have three sample size calculations, resulting in required sample sizes of 28, 16, and 48 patients, respectively, and when considering the risk of drop-outs, we estimate to include a total of approximately 80 patients. This is based on the inclusion schedule, where the required 48 evaluable patients finalizing all data for the outcome parameters have to be completed, will require an inclusion larger than 48 patients. This is because there will be 8 weeks from inclusion to obtaining the data point at two weeks after ended radiation therapy. Thus, we will include continuously in randomized blocks (see randomization above) until patient 48 has completed the 8 weeks data point. If we get less than 24 patients in one group completing the 8-weeks data point, additional blocks will be included, until we have at least 48 patients. The staff-member responsible for the randomization sequence will inform the investigators how many patients they will need to include to reach this point because of the randomization of the block size. During 2016, Rigshospitalet treated 194 patients who matched our inclusion criteria. Therefore we find it feasible to finish inclusion in approximately 6 months.

Statistical analyses

Normality of data will be assessed through visual inspection of histograms and Q-Q plots. Normally distributed data will be analyzed with parametric tests (e.g. unpaired t-tests), and not normally

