distributed data will be analyzed with non-parametric tests (e.g. Mann-Whitney U test). Our primary outcomes are the RTOG scores and the image analysis two weeks after the last radiation fraction, as well as the QLQ-BR3 breast symptoms on the last day of radiation therapy. Our secondary outcomes will be analyzed as follows: We will analyze steroid usage through two different outcomes. Days of steroid usage will be analyzed through either parametric or non-parametric tests. Any steroid usage (yes/no) will be analyzed through χ^2 or Fisher's Exact test. The RTOG scores, the quality of life questionnaires, and the image analysis values for the entire period will be analyzed in a mixed linear model, which takes correlation between patients into account. Subgroup analyses will be performed for mastectomized and lumpectomized patients respectively, if feasible. Other subgroup analyses may be performed based on background variables (fractionation schedule, histopathology and demographic data). Missing data will be taken into consideration when using the mixed linear model. A detailed statistical analysis plan will be formulated and be supervised by a bio-statistician prior to study start.

Data management

All outcomes will be collected by the primary investigator at time points listed in table 3. All data entered into the electronic case report form (eCRF) will be validated through “required fields” and format (e.g. date-format) where applicable. In the clinical photographs, patients will be marked with patient-ID written on tape, fixed to the patients’ chest. The time-stamp of the photograph will be noted in the eCRF. a*-values will be imported into the eCRF.

Our data will be stored electronically in Research Electronic Data Capture (REDCap), an electronic database used throughout the Capital Region of Denmark. All confidential data will be stored in a secure server for 15 years after patient enrollment in the study. Only the investigators and the Good Clinical Practice (GCP) Unit will have access to these data. After conclusion of the study, a final anonymized dataset will be available to RepoCeuticals ApS who has sponsored the

study through a grant through a formalized research contract between the Capital Region of Denmark and the company. Ownership of data is shared between the investigators and RepoCeuticals ApS.

Monitoring

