The study will be performed in accordance with the Helsinki II declaration. Patients will be included after oral and written consent. If patients do not wish to participate in the study, or choose to withdraw before administration of melatonin in any of the series of radiation therapy, they will receive standard treatment for their cancer. Patients can withdraw from the study at any time without stating a reason. Withdrawal from the study will not have any consequence for further treatment. Should an investigator deem it necessary for the safety of the patient, they can withdraw the patient from the trial. It is important to clarify if melatonin has a protective effect against

radiation injury, due to it having a large impact on the quality of life in patients. Positive results from this study will guide further studies and potentially change current practice in radiation oncology. The protective effect of melatonin has the potential to be used in several other types of cancer treatment, where ionizing radiation is used, to minimize the radiation injury and therefore decreased quality of life in patients. All information regarding participants in this study will be kept protected and no personal data will be published. The anonymity of all participants will be secured and data kept confidential.

Insurance

For this study no additional insurance policies have been arranged that exceed the *Danish Act on the Right to Complain and Receive Compensation within the Danish Health Service*

(Patientforsikringsloven). Patients participating in this study will be covered by the mentioned Act in accordance with “Bekendtgørelse af lov om klage- og erstatningsadgang inden for sundhedsvæsenet” in the same way as patients that are treated otherwise in the hospital. This is normal practice for investigator-initiated trials in Denmark.

Approvals

The study will be performed in accordance with the Helsinki II declaration. Approval from Danish Data Protection Agency in the Capital Region of Denmark (Datatilsynets fællesanmeldelse i Region H) will be sought in accordance with Data Protection Act (Databeskyttelsesloven), and the study will not start subject accrual before this approval has been given. The same applies for the local ethics committee as well as Danish Medicines Authority (Lægemiddelstyrelsen). Permission will be

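### Three primary outcomes, each sized at a full 5% alpha, with no success rule or multiplicity control: if any one significant result counts, the family-wise error is about 8-14%

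*Combined protocol and SAP*

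**What the plan says.** The Primary outcomes section describes the RTOG skin score, the a*-value from image analysis of photographs, and the QLQ-BR23 breast symptom score. Of the last it says "we focus on breast symptoms as a primary outcome". The text there calls RTOG the primary outcome in the singular, but under a plural heading. The Statistical analyses section then lists all three: "Our primary outcomes are the RTOG scores and the image analysis two weeks after the last radiation fraction, as well as the QLQ-BR3 breast symptoms", with breast symptoms taken on the last day of radiotherapy.

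Under Sample size calculations the protocol states "we have performed 3 separate sample size calculations", each with alpha 5% and beta 20%. The total is taken from the largest: "Because we have three sample size calculations, resulting in required sample sizes of 28, 16, and 48 patients, respectively". Allowing for drop-outs and for recruitment that continues during follow-up, "we estimate to include a total of approximately 80 patients".

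The Statistical analyses section gives no test level or sidedness, and no section gives an adjustment, a testing order or a definition of a positive trial. On further detail it says only "A detailed statistical analysis plan will be formulated and be supervised by a bio-statistician prior to study start". That document is not among those available, and the sentence does not say that it will cover multiplicity. The Dissemination policy puts RTOG and image analysis in one article and quality of life in another, and commits to publication whatever the result.

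**The concern.** With three co-equal primary outcomes, the error rate and the power of the trial depend on which pattern of results counts as success. The protocol leaves this open, and the two natural readings behave differently.

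- **Any one suffices.** Three tests at 5% give a false-positive chance above 5%. The protocol does not state this rule, but nothing excludes it, and separate articles leave room for each to claim success at its own 5%.
- **All three are required.** The error is controlled, but 80% power per outcome is not 80% power for the trial.

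The Study design section calls the trial pivotal, and Ethical considerations says "Positive results from this study will guide further studies and potentially change current practice in radiation oncology". A positive result therefore has to be defined. Publishing every result limits selective reporting, but it does not say which combination of three results is positive. A rule chosen once the comparisons have been seen cannot restore the error rate.

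**Working it through.** **1. Was alpha divided?** The inputs are from Sample size calculations, with normal formulas per group, z = 1.960 (two-sided 5%) and 0.842 (80% power).

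- RTOG, 90% v 41%, mean proportion 0.655: [1.960·√(2·0.655·0.345) + 0.842·√(0.9·0.1 + 0.41·0.59)]² / 0.49² = 13.5. The protocol states 14.
- Image a*, difference 18.4 − 13.44 = 4.96, placebo SD 3.47: 2·(3.47·2.802/4.96)² = 7.7. The protocol states 8.
- Breast symptoms, difference 82.2 − 70 = 12.2, SD 15.1: 2·(15.1·2.802/12.2)² = 24.0. The protocol states 24.

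The same formulas one-sided give 10.5, 6.1 and 18.9. The stated sizes therefore fit an undivided two-sided 5% for each outcome. The sidedness is inferred, because the protocol does not state it.

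**2. Any-one reading, no true effect on any outcome.** Independent outcomes: 1 − 0.95³ = 14.3%. Melatonin direction only: 1 − 0.975³ = 7.3%. The upper bounds are 3 × 5% = 15% and 3 × 2.5% = 7.5%. The correlated cases come from 2,000,000 trivariate normal draws per setting. The correlations are assumptions.

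| Pairwise correlation | Two-sided | Melatonin direction only |
|---|---|---|
| 0 | 14.3% | 7.3% |
| 0.3 | 13.6% | 6.8% |
| 0.5 | 12.5% | 6.3% |
| 0.7 | 10.9% | 5.5% |
| 0.9 | 8.4% | 4.2% |
| 0.8 for RTOG and a*, 0.3 with breast symptoms | 12.1% | 6.1% |

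The last row is included because independence is unlikely for RTOG and a*: the protocol itself links them through "erythema being a part of the RTOG acute radiation morbidity scoring criteria grade 1 and 2".

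**3. All-three reading.** Under the planned effects at 24 per group, power is 97.3% for RTOG (chi-square on 90% v 41%), above 99.9% for a*, and 78.2% for breast symptoms (exact t-test). If independent, the product is 0.973 × 0.9999 × 0.782 = 76%. Simulation gives 75.5% at correlation 0.3 and 75.9% at 0.7. Assuming independence, joint power is 80% at 26 per group, 88% at 32 and 94-95% at 40.

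**4. Cost of Holm.** Holm tests the smallest p-value at 0.05/3, the next at 0.05/2 and the last at 0.05.

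- All planned effects present, 24 per group, correlation 0.3, 60,000 simulated trials: breast symptoms 77.9% to 77.6%, RTOG 97.3% to 96.7%, a* above 99.9%.
- Only breast symptoms respond: this outcome must in practice pass 0.05/3. Exact t-test power at 5% and at 5%/3:

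| Per group | 5% | 5%/3 |
|---|---|---|
| 24 | 78.2% | 62.5% |
| 32 | 88.9% | 77.7% |
| 40 | 94.6% | 87.5% |

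At 5%/3, 33 per group gives 79.2% and 34 gives 80.6%, so 34 is the smallest size that reaches 80%.

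**5. Sensitivity to the RTOG test.** With Fisher's exact test for RTOG at correlation 0.3, the any-one error is 10.8% instead of 13.6%, and joint power is 73.3%.

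**The case against.** The strongest reply is that the protocol promises a detailed SAP with biostatistical supervision before the study starts, and that the primary investigator analyses the data blinded. The missing rule may already exist. This is a fair limit on the finding, which is that no rule is stated in the available documents. It does not remove the point: the promise does not mention a success rule, and the sample size in the protocol already depends on one. Blinding to group labels still leaves the p-values visible, so the rule must precede any comparison of outcomes.

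It can also be said that the 8-14% depends on a rule the protocol never states and counts errors in both directions. Both are true. The figure is conditional, and the melatonin-only error is 4.2-7.3% against 2.5%, which is still above nominal.

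Three technical objections stand as qualifications.

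- **Joint power.** The 75-76% applies at the minimum of 24 per group. Two more evaluable patients per group restore 80%.
- **Sidedness.** The inference is weaker outcome by outcome. A one-sided, continuity-corrected RTOG calculation gives 14.3, and the image figure depends on which SD is used. Breast symptoms discriminate clearly, and no one-sided formula tried reproduces all three sizes together.
- **RTOG test.** The power figures treat RTOG as a proportion, as the sample size does. The analysis text does not specify a chi-square test for RTOG and offers only its general choice between parametric and non-parametric tests.

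**Conclusion.** The concern holds and must be fixed. The protocol names three primary outcomes, sizes each at an undivided 5%, and states no success rule, order or adjustment. Followed as written, that means three unadjusted tests. If any one counts, the two-sided family-wise error is about 8-14% for assumed common correlations from 0.9 down to 0, and 12.1% in the mixed case that links RTOG and a*. If all three are required there is no inflation, but joint power at 24 per group is about 75-76% under the planned effects. The singular reference to RTOG does not settle the matter, because the other sections name all three as primary. Confidence is high that no rule is stated. The exact size of the inflation depends on correlations that the documents do not give.

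**What to change.** Before unblinding, and before any outcome is compared between groups, add one paragraph to the protocol and carry it into the promised SAP:

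- Claim efficacy on any primary outcome that is significant under Holm's procedure across the three, at a two-sided family-wise 5%. A fixed testing order named in advance would also control the error. If all three are meant to be required, say so and give the joint power.
- State the test level, the sidedness and the test for each primary outcome.
- Apply the rule jointly across the planned articles.
- Restate power under the chosen rule, including the case where only breast symptoms respond.

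The drafting cost is small. The real cost of Holm is breast symptom power of about 62% at 24 per group when the other two outcomes show no effect. Restoring 80% in that case takes about 34 evaluable patients per group, 68 in total. This fits within the approximately 80 planned inclusions if no more than (80 − 68)/80 = 15% are lost. Otherwise the lower power has to be accepted and stated.

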Melatonin has the disadvantage of being unstable when exposed to air and light. A study demonstrated that melatonin in aqueous solutions at room temperature, and at neutral pH, degrades by 29% over 21 days [26]. The compound dimethyl sulfoxide (DMSO) has seen wide use both as a solvent and as an anti-inflammatory drug [27, 28]. Based on a report made available to the authors from the pharmaceutical company, Bioneer A/S, melatonin dissolved in DMSO undergoes no degradation over 45 days when stored at 25 °C temperature, away from light.

The aim of the present randomized double-blinded placebo-controlled clinical trial is to investigate if melatonin can protect against acute radiation dermatitis in patients with early breast cancer receiving radiation therapy, and whether this has an impact on the patients' quality of life.

Study design

The study is registered at clinicaltrials.gov (indsæt ID, når dette er sket). This is protocol version 1.0, 13/09/2018. The study will be a randomized, placebo-controlled, double-blinded clinical pivotal trial. Patients will be allocated in a ratio of 1:1 to the melatonin or placebo group. Patients will be stratified according to the type of surgery (lumpectomy or mastectomy). Randomization will be performed in blocks of randomized sizes. The study will be performed in the Department of

Oncology, Rigshospitalet, Denmark. Patients will be included into our study according to specific eligibility criteria (see Table 1).

Interventions

Eligible patients with early breast cancer receive adjuvant radiation therapy over 15 to 30 daily fractions (5 fractions per week) of ionizing megavoltage photon radiation to a total of 40 - 60 Gy within 3-5 weeks according to the guidelines of the Danish Breast Cancer Cooperative Group [29].

In our study, the patients will administer approximately 1 g of cream containing melatonin (25 mg/g) and dimethyl sulfoxide (DMSO) (150 mg/g) or a placebo cream topically twice daily on the irradiated skin area. They are scheduled to do this every day from the first to the last fraction of radiation therapy, including the days where they do not receive radiation therapy. We have chosen placebo as our comparator due to it being safe, and in our view the most reasonable method of evaluating any effects of the intervention. On days where the patients receive radiation, the melatonin/DMSO or placebo cream will be applied no less than 2 hours prior to radiation.

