If a patient does not wish to complete all three follow-up visits, some of the outcomes can be filled in electronically from home, should the patients wish to do so. These outcomes are the QLQ-C30 and QLQ-BR23 questionnaires, and steroid usage outcomes. All data from drop-outs will be used in statistical analyses. Discontinuation of treatment will only occur in the following eventualities: the patient withdraws consent, or if the sponsor decides to terminate the study due to serious adverse events.

Conclusion of study

Recruitment of patients will be concluded when 48 patients have completed the study (see sample size calculations below, in the “Statistics” section). The study will be concluded, when all patients included have completed the study.

Handling of drugs

Storage

The active cream will consist of 25 mg/g melatonin as well as 150 mg/g DMSO, in a cream base. The placebo will consist of just the cream base. The cream base consists of polysorbate 80 (0,5%), cetostearyl alcohol (5%), paraffin oil (5%), glycerol monostearate 40-50 (6%), methyl

parahydroxybenzoate (0,1%), glycerol 85% (4%), sorbitol (7%), purified water (72,4%). The dose for each application will be 1 g, and the cream will be packaged in 30 g tubes. The tubes will be stored at room temperature, in a locked cabinet, in the office of one of the investigators. The cream will be produced and packaged by Glostrup Apotek in their manufacturing facility, according to EU GMP-guidelines. The tubes will be labelled with all required information listed in the EU GMP-guidelines concerning investigational medical products. All drugs will be delivered directly to the sponsor, who will document receiving the products according to GCP-guidelines (modtagekontrol).

Patients will be given one tube of cream at a time, and a second and third tube will be given to them, once the previous tube is empty or running low. Patients will be instructed to keep the tubes out of reach of children, away from sunlight and at room temperature. These instructions will also be listed on the label of the cream.

Administration

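### Neither steroid outcome takes account of time observed, and no rule says how patients with incomplete follow-up are counted.

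*Combined protocol and SAP*

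**What the plan says.** All references are to the combined protocol and SAP.

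- **Statistical analyses** defines two steroid outcomes. For the first, "Days of steroid usage will be analyzed through either parametric or non-parametric tests". For the second, "Any steroid usage (yes/no) will be analyzed through" chi-square or Fisher's exact test.
- **The same section** gives one missing-data provision: "Missing data will be taken into consideration when using the mixed linear model". The scope of that model is also stated: "The RTOG scores, the quality of life questionnaires, and the image analysis values for the entire period will be analyzed in a mixed linear model". Steroid use is not among these outcomes.
- **Drop-outs and patient retention** says "All data from drop-outs will be used in statistical analyses". It also lets patients who do not wish to complete the three follow-up visits report some outcomes electronically from home: "These outcomes are the QLQ-C30 and QLQ-BR23 questionnaires, and steroid usage outcomes".
- **Secondary outcomes** sets the assessment times: "Patients will be asked about steroid cream usage for radiation dermatitis at baseline, once weekly during radiation therapy, and once weekly for three weeks after". Those three weeks are counted from the end of radiotherapy.
- **Interventions** describes "adjuvant radiation therapy over 15 to 30 daily fractions", so the period over which days are counted differs between patients. Randomization is stratified by type of surgery only.
- **Statistical analyses** also promises a detailed analysis plan before study start. It is not part of the documents reviewed.

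**The concern.** A t-test, Mann-Whitney, chi-square or Fisher test takes one value per patient and has no term for length of observation. Steroid days and any use can only accumulate with time, so shortened observation can lower them but never raise them. The sample size section expects erythema to be worst about two weeks after radiotherapy ends. A patient lost during radiotherapy is therefore lost before the period in which need is expected to be greatest.

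Unequal withdrawal is possible. The active cream contains DMSO and the placebo is the cream base alone. The Harms section lists a garlic-like odor and, at much larger topical doses, mild burning. Patients may leave at any time without giving a reason.

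At stake is a treatment comparison that the Dissemination policy assigns to the dermatitis article, alongside RTOG and image analysis. Differential loss could create a false difference in steroid need or hide a real one. Even equal loss would shrink a real difference.

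**Working it through.** **1. Figures in the plan.** The documents give no rate, SD, power or sample size for either steroid outcome, and no drop-out rate. The governing sample size comes from breast symptoms: 2 × (1.96 + 0.84)² × (15.1/12.2)² ≈ 24 per group, which agrees with the plan's 24. Steroid use plays no part in it. The calculations below use 40 per arm (the planned 80, split 1:1). All steroid and withdrawal rates are assumptions.

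**2. Any use.** Let p be the true proportion who would use steroid, d the proportion withdrawing, and f the share of withdrawn would-be users who leave before first use. If unobserved use is counted as none, the observed proportion is p × (1 − d × f). Test properties are by exact enumeration at a nominal 5%, chi-square without continuity correction.

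*Equal withdrawal, d = 20%, f = 1, true 50% versus 25%:*
- Observed: 0.50 × 0.80 = 40% and 0.25 × 0.80 = 20%. The difference falls from 25 to 20 points.
- Chi-square power falls from 65% to 50%.
- With no true effect (50% in both arms), the type I error is 5.2% for chi-square and 3.0% for Fisher. No false difference is created.

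*Unequal withdrawal, no true effect:*

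| True use | Withdrawal | f | Observed | Chi-square | Fisher |
|---|---|---|---|---|---|
| 50% | 20% vs 10% | 1 | 40% vs 45% | 7.9% | 4.9% |
| 50% | 30% vs 10% | 1 | 35% vs 45% | 15.4% | 10.5% |
| 50% | 30% vs 10% | 0.5 | 42.5% vs 47.5% | 8.0% | 5.0% |
| 30% | 30% vs 10% | 1 | 21% vs 27% | 9.6% | 6.1% |

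The last two columns are type I error.

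**3. Steroid days.** This is a simulation with no true effect, 50% users, onset on days 14 to 42 and duration 7 to 21 days. Withdrawal of 30% versus 10% gives means of 5.6 and 6.5 days. The type I error is 8.1% (t-test) and 7.4% (Mann-Whitney), against about 4% with no withdrawal.

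**4. Counting window among completers.** At five fractions a week from a Monday, 15 fractions span 19 calendar days and 25 span 33. Adding 21 days of follow-up gives 40 and 54 days, a ratio of 1.35. Thirty fractions at this rate would span 40 days, giving 61 in all. That is six weeks of treatment, while the same section gives a range of three to five weeks. The documents need to reconcile this.

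**5. Does a time-aware analysis help?** Same assumptions as step 3, with withdrawal 30% versus 10%.

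- *Withdrawal unrelated to steroid need:* raw any use is 42% versus 47%, and Kaplan-Meier gives 50% versus 50%. The ratio of mean steroid days is about 0.87. Dividing by observed time moves it to between 0.94 and 0.97, depending on simulation details.
- *Only would-be users withdraw, before first use:* raw any use is 20% versus 40%, and Kaplan-Meier gives 27% versus 44%. The ratio for days moves from 0.50 to 0.60.

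Censoring therefore removes the bias in any use in the first case and only part of it in the second. Dividing days by observed time is a partial correction in both, because it treats need as constant over time.

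**6. Counting withdrawals before first use as users.** In the second case this gives 20% + 30% = 50% and 40% + 10% = 50%, which is the truth. In the first case it adds non-users as well: 42% + 8% + 15% = 65% versus 47% + 3% + 5% = 55%. It is a bound to set beside the main analysis, not a replacement for it.

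**The case against.** The strongest reply is that the plan contains no biased coding rule. Using all data from drop-outs most directly means using what was observed, and treating later weeks as missing fits that sentence as well as treating them as zero. A reader might infer that the plan scores withdrawn patients as non-users. The text does not say so. This stands, and the defect is an absent rule combined with tests that cannot use observation time.

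Steroid use is also one of the few outcomes that can be reported from home. That does reduce the loss. However, it is voluntary, is offered only in place of follow-up visits, and does not reach a patient who withdraws consent during radiotherapy.

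A reader might also infer that withdrawal necessarily biases the comparison, or that it favours one arm. Neither follows. A false difference needs unequal loss, and the documents give no evidence on its size or direction. Unequal radiotherapy length among completers is balanced in expectation by randomization, so it mainly adds noise to the day count.

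The promised detailed analysis plan is a suitable place for the missing rule, but it cannot be credited with content that the documents do not show. Finally, log-rank and Kaplan-Meier methods assume uninformative censoring. That objection is correct, and it is why a sensitivity analysis is needed as well.

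**Conclusion.** The point holds in a limited form. Both steroid outcomes are analysed without regard to time observed, drop-out data are included, and the missing-data provision does not extend to steroid use. Followed as written, the plan allows early withdrawal to lower recorded use.

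Under the assumed rates, equal 20% loss costs about 15 percentage points of chi-square power. Loss of 30% versus 10% raises the type I error to about 15% (chi-square) or 10.5% (Fisher) if every withdrawn would-be user leaves before first use. If only half do, the figures are 8.0% and 5.0%. These results depend on assumed use and withdrawal rates and on unobserved use being counted as none.

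The planned 80 inclusions for 48 completers might be read as 40% expected loss (1 − 48/80). The plan attributes much of that excess to patients still in follow-up when the 48th completes, so 40% is an upper limit and not a drop-out forecast.

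It would be wrong to conclude that the trial's main result is threatened. The outcomes are secondary, and the primary outcomes and sample size are unaffected. The change is worth making before unblinding, but the trial does not depend on it.

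**What to change.** In the Statistical analyses section, or in the promised detailed plan:

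1. Analyse any steroid use as time from first fraction to first steroid use, censored at the last completed steroid assessment. Use Kaplan-Meier curves and a log-rank test stratified by type of surgery, to match the randomization.
2. Define the counting window for steroid days and report them relative to the days on which steroid status is known. State that unobserved days are not coded as zero. Note that this corrects only partly if need is concentrated late.
3. Add a sensitivity analysis that counts patients who withdraw before first use as steroid users, and report it beside the main result as a bound.
4. Record the date of first steroid use.

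The cost is plan wording, slightly more analysis work and one eCRF date field. Steroid use is already asked about weekly, so no visits are added. Days relative to observed time are a little harder to explain than a simple count.
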